2. HIV
3. Planning to go for breast enhancement or gender reassignment surgery in the next 6 months
4. Known history of peanut allergy (because the study drug contains peanut oil)
5. Active deep vein thrombosis, pulmonary embolism or history of these conditions
6. Active arterial thromboembolic disease or history of these conditions
7. Active cardiovascular disorders or history of these conditions (e.g. myocardial infarction, uncontrolled hypertension >150/90 mmHg)
8. Known, suspected, or history of breast cancer
9. Known liver dysfunction or disease
10. Known or history of gallbladder disease. This does not apply to subjects who have undergone cholecystectomy
11. Known or history of hypertriglyceridemia (>400 mg/dl)

**Screening visit:** Informed consent will be obtained. This visit may be conducted during the PI's clinic (if the study volunteer is PI's patient) or at Endocrinology clinical research space at Salus Center. Vital signs (blood pressure, heart rate and weight) will be measured and a general physical examination will be performed.

Subjects who qualify and consent to take part in the study will be assigned a number by a computerized random number generation program and will be randomized (1:1) to receive either progesterone or placebo. An unblinded pharmacist will prepare the study product. Study investigators, staff and the study participants will be blinded.

**Week 0 (baseline):** Subjects will come fasting to the Salus Center. Breast exam and testicular exam will be conducted. They will complete the study questionnaires. Blood sample will be taken for total testosterone, total estradiol, sex hormone binding globulin (SHBG), LH, FSH, complete blood count (CBC), comprehensive metabolic panel (CMP) and research labs. For subjects who are on intramuscular estradiol, this visit will be performed 3-4 days after their last injection. Subjects will be randomized to receive generic micronized progesterone 200 mg or placebo tablets, to be taken at bedtime daily. They will be given a 3-month supply of the study drug. Subjects will be asked to bring the pill bottles back with them at the next visit to assess compliance.

**Week 4:** Subjects will be called by the study coordinator to counsel on drug compliance and to ask for side-effects.

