**Week 12:** Subjects will come fasting to the Salus Center. For subjects who are on intramuscular estradiol, this visit will be performed 3-4 days after their last injection. Vital signs (blood pressure, heart rate and weight) will be measured and a general physical examination will be performed. Blood sample will be taken to measure total testosterone, total estradiol, SHBG, LH, FSH and research labs. They will complete the study questionnaires. They will be given a 3-month supply of the study drug. Subjects will be asked to bring the pill bottles back with them at the next visit.

**Week 24 (end of study):** Subjects will come fasting to the Salus Center. For subjects who are on intramuscular estradiol, this visit will be performed 3-4 days after their last injection. Blood sample will be taken to measure CBC, CMP, total testosterone, total estradiol, SHBG, LH, FSH and research labs. Vital signs (blood pressure, heart rate and weight) will be measured and a general physical examination will be performed. Breast exam and testicular exam will be conducted. They will complete the study questionnaires. They will then be discharged from the study.

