- b) Symptom-Checklist-K-9 (SCL-K-9) to measure psychological distress level(20): This questionnaire has 9 questions and is meant to assess overall psychological distress. Responses are recorded on a 5 point Likert scale. The mean of all 9 questions is presented as the global severity index.

*Sleep quality:* We will use single-item sleep quality scale (SQS) to assess change in sleep quality during the study.

FG score calculator and study questionnaires are attached in the IRB application.

*Research labs:* 10 ml of blood will be obtained for research. Serum will be stored for future analysis based on study results. For example, if there is a decrease in FG score, we will check dihydrotestosterone levels.

**Side effects:** Progesterone may cause fluid retention, mood swings, breast tenderness, depression, transient dizziness and drowsiness, headache, abdominal pain or bloating, hot flashes in women. Long term use is associated with possibly increased risk of heart disease and stroke in women after menopause. Short term and long term risks in transwomen are not known.

If a significant or serious adverse event occurs, the subject will cease participation in the study. Discovery of two or more patients experiencing a significant or serious adverse event will lead to stopping of this study altogether.

**Statistical analysis:** The primary end-point of the study is change in total testosterone concentrations in transwomen after progesterone treatment at 24 weeks as compared to placebo. Transformations of the

data to meet statistical assumptions may be considered. *t*-test will be used for comparison. We estimate that testosterone concentrations will decrease by 20%. A sample size of 20 subjects per group (assuming a drop-out rate of 15%) will provide adequate power ( $\beta = 0.8$ ) to detect a significant difference ( $\alpha = 0.05$ ), provided the pooled standard deviation is not greater than the mean difference. Hence, we will recruit 40 transwomen in this study.

*Secondary end-points:* Change at weeks 12 and 24 in a) LH and FSH concentrations, b) breast size, breast hemi-circumference, areolar diameter, Tanner stage, feeling of fullness in breast, bra cup size, c) FG score, shaving frequency, scalp hair growth, scalp hair quality, d) global severity index scores on BUT-BIC and SCL-K-9 scales, e) SQS score.

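### The plan lists a side-effect question only at the week 4 call of a 24-week treatment, and plans no adverse-event summary by arm

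*Combined protocol and SAP*

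**What the plan says.** The Side effects paragraph names nine effects of progesterone. It begins "Progesterone may cause fluid retention, mood swings, breast tenderness, depression, transient dizziness and drowsiness" and goes on to headache, abdominal symptoms and hot flashes. For the population under study it says "Short term and long term risks in transwomen are not known".

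Two rules act on adverse events. A participant who has a significant or serious event leaves the study, and "Discovery of two or more patients experiencing a significant or serious adverse event will lead to stopping of this study altogether". The word *significant* is not defined.

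The visit schedule is itemised. At week 4, "Subjects will be called by the study coordinator to counsel on drug compliance and to ask for side-effects". At weeks 12 and 24 the listed items are blood sampling, questionnaires and an examination: "Vital signs (blood pressure, heart rate and weight) will be measured and a general physical examination will be performed". Week 24 adds CBC, CMP, and breast and testicular examination. Neither visit lists a question about side effects. The week 12 entry reads "They will complete the study questionnaires. They will be given a 3-month supply of the study drug", and the week 24 entry ends "They will complete the study questionnaires. They will then be discharged from the study".

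The questionnaires described under Study Procedures are the BUT-BIC (body image), the SCL-K-9 (psychological distress) and the SQS (sleep quality), with separate items on breast fullness and hair. Their full content is elsewhere: "FG score calculator and study questionnaires are attached in the IRB application".

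The Study endpoints list and the Statistical analysis section cover hormones, breast, hair, mood and sleep. Neither plans a summary of adverse events, safety laboratory results or vital signs.

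**The concern.** A stopping rule that acts on discovery is only as good as the means of discovery. Here the one listed direct enquiry comes four weeks into daily dosing, and the participant is then treated for another 20 weeks. If staff follow the schedule as written, a symptom that starts in week 8 is recorded only if the participant mentions it or something shows on examination or in the blood.

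Two things are at stake. The first is the safety decision: the rule for stopping the study, and the rule for withdrawing a participant, may fail to act because no one asked. The second is the record: the trial would describe the tolerability of 24 weeks of progesterone largely from one enquiry at week 4, in a group whose risks the plan says are unknown. Symptoms not asked about at weeks 12 and 24 cannot be reliably recovered later, so no later analysis can repair this.

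**Working it through.** **What is asked, and when.** Dosing lasts 24 weeks and the listed enquiry is at week 4, so (24 − 4)/24 = 20/24 = 83% of the dosing period follows the last listed side-effect question.

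**What the later visits can pick up.** Of the nine named effects:

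- Fluid retention is partly covered by weight and physical examination.
- Mood swings and depression are partly covered by the SCL-K-9.
- The other six (headache, hot flashes, dizziness, drowsiness, breast tenderness, and abdominal pain or bloating) have no listed question after week 4.

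The SCL-K-9 and SQS are analysed as secondary endpoints, with no stated link to adverse-event recording. CBC and CMP are repeated only at week 24, when the participant is discharged.

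**Illustration of the possible loss.** The plan gives no event rates, so every rate below is an assumption. Let p be the risk of an event by week 24. With a constant rate, the risk by week 4 is p4 = 1 − (1 − p)^(4/24). If a share s of the later events comes to light, the risk of a *discovered* event is q = p4 + s(p − p4).

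*Side effects in the progesterone arm (n = 20).* P(at least one case discovered) = 1 − (1 − q)^20.

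| p | p4 | Expected cases by week 4 / week 24 | s = 0 | s = 0.5 | s = 1 |
|---|---|---|---|---|---|
| 10% | 1.74% | 0.35 / 2 | 30% | 70% | 88% |
| 20% | 3.65% | 0.73 / 4 | 52% | 92% | 99% |

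For p = 20% and s = 0.5, q = 0.0365 + 0.5 × (0.20 − 0.0365) = 0.118, and 1 − (1 − 0.118)^20 = 0.92.

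*Stopping rule (both arms, n = 40).* P(two or more discovered) = 1 − (1 − q)^40 − 40q(1 − q)^39.

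| p | s = 0 | s = 0.5 | s = 1 |
|---|---|---|---|
| 5% | 5% | 33% | 60% |
| 10% | 15% | 69% | 92% |

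For p = 5%, p4 = 0.85%; with s = 0.5, q = 0.0085 + 0.5 × (0.05 − 0.0085) = 0.0293, which gives 33%.

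**Sensitivity to timing.** If half of all events start by week 4 and none of the later ones is found, q = p/2. The rule then fires with probability 26% at p = 5% and 60% at p = 10%. If every event starts by week 4, or every later one is volunteered, the figures are 60% and 92%, and nothing is lost.

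The s = 0 column is a bound, not a forecast: examinations, blood tests and volunteered reports will reveal some later events.

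**The case against.** The strongest objection is that the collection gap is inferred from silence. The questionnaires are not in the document, and a side-effect checklist among them would remove this part of the point. Consent pages have also been taken out, so any instruction to participants to report symptoms would not be visible. Weeks 12 and 24 are in-person visits with a physical examination, and a short protocol may not write out every question a clinician asks. This stands as a limit on the claim. Against it, the plan does state the question where it intends it, at week 4. Nothing under Study Procedures describes a side-effect checklist. Questions left to habit may also vary between visits and would be a poor basis for a by-arm summary.

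The second objection concerns the stopping rule. The six unasked effects are mostly mild, and the rule concerns significant or serious events discovered by any route. That is right: nothing shows that these symptoms would be the rule's main input. Some effects may also appear soon after dosing starts and be caught at week 4; the plan itself describes the dizziness as transient.

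Two stronger readings do not hold. A reader might infer that no safety outcome is compared by arm. That is too broad, because change in the SCL-K-9 score is a named secondary endpoint and bears on two of the listed effects. What is absent is any planned summary of adverse events, laboratory safety or vital signs. A reader might also take the lowest figures above as the expected performance of the rule. The documents do not support that, since they give no event rates and provide other routes of discovery.

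**Conclusion.** The concern holds in a limited form. As written, the plan prompts for side effects once, at week 4 of 24, while calling the risks in this population unknown and tying the trial's continuation to two discovered events. Unless the unseen questionnaires contain a side-effect checklist, tolerability after week 4 will be under-recorded. The size of the loss cannot be derived from the documents: it runs from none upward, and the illustrative figures rest on assumed event rates, a constant rate over time and an assumed share of later events found.

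The absence of a planned adverse-event, laboratory or vital-sign summary does not depend on what the questionnaires contain, but taken alone it is mostly missing detail. The testosterone and breast results are unaffected. The change should be made because the data must be collected prospectively and the remedy is cheap.

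**What to change.** 1. Repeat the week 4 question at the existing week 12 and week 24 visits, and ask it of anyone who withdraws. Use one short checklist of the nine effects in the Side effects paragraph plus an open question, in the same form each time. If the IRB questionnaires already include such a checklist, say so in the protocol.
2. Define *significant* before the first dose, for example as an event that needs medical treatment or stopping the study drug.
3. Add a sentence to the Statistical analysis section: adverse events, CBC and CMP results, and vital signs will be summarised descriptively by arm.

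The cost is a few minutes at two visits already held, one form and one sentence; no new visit, assay or staff is needed.

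There are two drawbacks. Asking more often finds more events, so the two-patient rule may fire more often, including on background events unrelated to the drug: at an assumed 5% event rate in both arms it fires with probability 60% when all are found. That is why item 2 has to accompany item 1. The by-arm summary will also be imprecise at 20 per arm. For example, 6/20 against 2/20 is a difference of 20 percentage points with a 95% interval from −5 to 43 (Newcombe), and 0/20 leaves an upper 95% limit of 17% (Clopper-Pearson). It should be presented as description, not as a test.

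### A participant with a significant or serious adverse event before week 24 leaves the study, not just the drug, so the plan as written does not collect that person's week-24 testosterone or only scheduled post-baseline CBC/CMP

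*Combined protocol and SAP*

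**What the plan says.** The Side effects paragraph under Study Procedures sets a rule for the individual, "If a significant or serious adverse event occurs, the subject will cease participation in the study", and a rule for the trial, "Discovery of two or more patients experiencing a significant or serious adverse event will lead to stopping of this study altogether". The same paragraph says of progesterone: "Short term and long term risks in transwomen are not known". It does not define a significant event, and nothing in the document separates stopping study drug from leaving the study.

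The visit schedule, in order:

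- **Week 0:** the blood sample includes "complete blood count (CBC), comprehensive metabolic panel (CMP) and research labs".
- **Week 4:** a telephone contact only: "Subjects will be called by the study coordinator to counsel on drug compliance and to ask for side-effects".
- **Week 12:** vital signs, physical examination, questionnaires and hormones, without CBC or CMP: "Blood sample will be taken to measure total testosterone, total estradiol, SHBG, LH, FSH and research labs".
- **Week 24:** "Blood sample will be taken to measure CBC, CMP, total testosterone, total estradiol, SHBG, LH, FSH and research labs". After this visit, "They will then be discharged from the study".

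The Statistical analysis section makes the week-24 change in total testosterone the primary endpoint, compared by t-test. It plans 20 per group with a 15% drop-out allowance and permits transformation of the data. It names no analysis set and no method for missing values.

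**The concern.** Stopping study drug protects the participant. Ending participation also ends data collection, and the protection does not need that. The person removed is the one with the event, removed after randomisation for a reason that may be linked to treatment. The t-test on week-24 change would then leave that person out, so the comparison is no longer of everyone randomised.

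The safety record has a matching gap. CBC and CMP are scheduled only at weeks 0 and 24, so this participant has no scheduled value after baseline, in a plan that calls the risks in this population unknown. If the event comes before week 12, the week-12 hormones, vital signs and examination are lost as well.

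**Working it through.** **Inputs.** From the Statistical analysis section: 20 per group, 15% drop-out, alpha 0.05, target power 0.80 (printed as beta), expected fall 20%, and a pooled SD no larger than the mean difference, so a standardised difference d = 1 at the limit. From the Screening visit section: 1:1 allocation. Sidedness is not stated; two-sided is assumed.

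**The plan's own figure.** A two-sample t-test (noncentral t) with d = 1 and power 0.80 needs 16.7, so 17 per group. 17/(1 − 0.15) = 20. The stated 20 per group reproduces. The allowance is 0.15 × 20 = 3 per arm, leaving 17 v 17 and power 0.807.

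**How many can be lost.** The trial stops once two participants have such an event, so a trial that reaches its planned end has lost at most one. The documents give no event rate. Assuming independent events with probability p among 40, the chance of exactly one is 40p(1 − p)^39:

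| Assumed p | Exactly one | Two or more (study stops) |
|---|---|---|
| 1% | 27% | 6% |
| 2% | 36% | 19% |
| 5% | 27% | 60% |

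**Effect of leaving out one progesterone participant.** The others average a 20% fall; the person omitted would have had either twice that fall (40%) or none.

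| Progesterone arm | Omitted fall 40% | Omitted fall 0% | Power at d = 1 |
|---|---|---|---|
| 18 → 17 (within the allowance) | (18 × 0.20 − 0.40)/17 = 18.8% | 18 × 0.20/17 = 21.2% | 0.81 (17 v 17) |
| 17 → 16 (on top of the allowance) | (17 × 0.20 − 0.40)/16 = 18.8% | 17 × 0.20/16 = 21.3% | 0.79 (16 v 17) |
| 20 → 19 (no other drop-out) | (20 × 0.20 − 0.40)/19 = 18.9% | 20 × 0.20/19 = 21.1% | 0.86 (19 v 20) |

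**Effect of keeping that person, off drug.** If the full effect remains at week 24, power is 0.82 (18 v 17) or 0.81 (17 v 17). If none remains:

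- 18 v 17: estimated fall 0.20 × 17/18 = 18.9%. Power at d = 17/18 is 0.774, or 0.765 by simulation that also counts the added variance.
- 17 v 17: estimated fall 0.20 × 16/17 = 18.8%. Power at d = 16/17 is 0.758, or 0.748 by simulation.

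This is not an upper bound on the cost. Participants take estradiol, which the introduction says is given partly to suppress testosterone. Suppose (an assumption) that the event also leads the clinician to stop estradiol, and testosterone rises above baseline. Simulation with 18 v 17, SD 20 points and untransformed values gives:

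| Kept person's change | Estimated fall | Power |
|---|---|---|
| 0% | (17 × 20 − 0)/18 = 18.9% | about 0.77 |
| +50% | (17 × 20 − 50)/18 = 16.1% | 0.51 |
| +100% | (17 × 20 − 100)/18 = 13.3% | 0.19 |

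**The case against.** The strongest case against acting is that the loss is at most one person, the drop-out allowance can absorb it, and keeping the person can cost the primary test more than losing them. On the figures above that is right: omission leaves power at 0.79 to 0.81, while one large off-drug rise could take it to 0.51 or lower. The endpoint can also be read as a pharmacological question, to which an off-drug value is less relevant, so preferring the as-randomised comparison is a choice of estimand. These points stand. They are why the severity is minor and why an on-treatment analysis belongs beside the primary one. The transformation that the plan permits could also soften the influence of a single high value.

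The safety gain is modest too. A week-24 CBC/CMP shows status at week 24, not at the time of the event. And the rule covers at most one of the roughly six drop-outs allowed for (3 per arm); the missing analysis set and missing-data method are a wider gap that this change does not close.

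A reader might infer that the protocol forbids any further sample, or that the event goes unfollowed. The text says neither. The loss of data follows from ending participation with no later visit described; unscheduled tests and clinical care outside the study are not excluded. Contacts before the event, such as the week-4 call or the week-12 visit, would still have taken place.

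**Conclusion.** The point holds as a cheap improvement of minor severity. Under the plan as written, an event before week 24 leaves that participant without the primary outcome and without any scheduled CBC/CMP after baseline. In a completed trial this affects at most one person and, under the assumptions shown, moves an expected 20% fall to between 18.8% and 21.3%.

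A reader might go further and conclude that the rule biases the primary result seriously or threatens the trial's validity. The two-participant stopping rule and the size of the shift do not support that. The benefit of a change is a comparison closer to as-randomised and later safety data on the person who had the event. It is not power. The power figures rest on d = 1, a two-sided test and roughly normal, untransformed changes; the event rates and any rise after stopping estradiol are assumptions.

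**What to change.** Replace the rule "If a significant or serious adverse event occurs, the subject will cease participation in the study" with wording such as:

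> If a significant or serious adverse event occurs, the subject will stop study drug and, with consent, attend the remaining planned visits (including week-24 testosterone, CBC and CMP).

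In the Statistical analysis section, add that the primary comparison includes all randomised participants with a week-24 value, each in the assigned arm, and that an on-treatment analysis without the off-drug value is shown as a sensitivity analysis. Record any change in background estradiol after the event, so that a rise in testosterone can be interpreted.

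The cost is a few sentences and up to two visits (weeks 12 and 24) that are already in the schedule, for one person. The sample size does not change. The statistical price is the possible dilution set out above, which the sensitivity analysis makes visible.

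### Two patients with a significant or serious adverse event, in either arm and from any cause, end the trial without a described review, and 'significant' is undefined

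*Combined protocol and SAP*

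**What the plan says.** The Side effects paragraph under Study Procedures contains two linked rules. For the individual: "If a significant or serious adverse event occurs, the subject will cease participation in the study". For the trial: "Discovery of two or more patients experiencing a significant or serious adverse event will lead to stopping of this study altogether". Both use the word *significant*, and neither defines it. Just before them, the paragraph lists expected effects such as mood swings, headache, dizziness and bloating, and states: "Short term and long term risks in transwomen are not known".

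The Screening visit paragraph sets 1:1 allocation and says who knows it: "An unblinded pharmacist will prepare the study product", and "Study investigators, staff and the study participants will be blinded". No section describes a monitoring committee, a medical monitor, a causality assessment, an unblinding procedure or a pause.

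The Statistical analysis paragraph makes the week-24 change in total testosterone the primary endpoint, tested by a *t*-test. On size it says "A sample size of 20 subjects per group (assuming a drop-out rate of 15%) will provide adequate power", "provided the pooled standard deviation is not greater than the mean difference".

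**The concern.** The trial has a placebo group, but the stopping rule does not use it. Those who apply the rule are blinded, so they cannot tell whether the two patients took progesterone. The wording does not ask whether the events had anything to do with the drug. Once the second patient is found, the stated consequence is termination.

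A stop caused by placebo-arm or unrelated events protects nobody from progesterone. It also leaves everyone still in follow-up without the week-24 testosterone value. The individual rule adds a smaller loss, because it ends participation and not only dosing, so the affected patient's week-24 value is lost too.

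The undefined word decides how large the problem is. If *significant* means little more than serious, the trigger should be rare. If it reaches troublesome cases of the listed side effects, the trigger could be common, and two investigators could apply it differently.

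**Working it through.** **Inputs from the documents.** 40 patients, 20 per group, 15% drop-out, alpha 0.05, power 0.80, standard deviation no greater than the mean difference (Statistical analysis); 1:1 allocation (Screening visit); threshold of two patients (Side effects).

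**Assumptions.** Alpha is two-sided (sidedness is not stated). The per-patient risk of a qualifying event over 24 weeks, *p*, is not given, so 1%, 2% and 5% are used. Events are independent between patients.

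**Step 1: the plan's sample size.** With a standardised difference of 1, the exact two-sample *t*-test needs 16.7, so 17 per group. Allowing for drop-out, 17 / 0.85 = 20 per group. The plan's figure is reproduced. Power at 17 per group is 0.807, so there is almost nothing to spare.

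**Step 2: chance that the rule is met.** P(X ≥ 2) = 1 − (1 − p)^n − n·p·(1 − p)^(n−1).

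For n = 40:
- p = 1%: 1 − 0.669 − 0.270 = 0.061
- p = 2%: 1 − 0.446 − 0.364 = 0.190
- p = 5%: 1 − 0.129 − 0.271 = 0.601

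For n = 34, treating the 15% who drop out as never at risk (a lower bound), the results are 0.045, 0.148 and 0.512. With n = 40 the chance reaches one half at p of about 4.2%.

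**Step 3: which arm the two patients come from.** If progesterone has no effect on events, the chance that both are on placebo is (20 × 19) / (40 × 39) = 0.244. The chance that both are on progesterone is the same, so at least one is on placebo with probability 1 − 0.244 = 0.756.

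**Step 4: power if a stop occurs.** Two-sample *t*-test, standardised difference 1, noncentrality √(n/2), by number per group with a week-24 value when the study stops:

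| Completers per group | Power |
|---|---|
| 17 | 81% |
| 15 | 75% |
| 12 | 65% |
| 10 | 56% |
| 5 | 29% |

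These are conditional on when the stop comes. They are not weighted by the chance of a stop.

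**Step 5: combining the two.** A simulation took 34 patients at risk, uniform accrual and event times, and affected patients left out of the analysis. Accrual length is not stated, so it was varied from near-simultaneous entry to 104 weeks. Overall power was 77–79% at p = 1%, 68–75% at 2% and 39–58% at 5%, against 81% with no stop and 17 completers per group. Given that a stop occurred, power was at most 45%.

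**The case against.** The strongest reply is that this is a deliberate and cautious rule. Risks in this population are stated to be unknown. Ignoring arm and cause means that nobody need be unblinded and no causality judgement is needed in a 40-patient study. Much of this stands: a threshold of two is defensible and is not disputed. However, pausing everyone at the second patient gives the same immediate protection, and ending the study remains possible after review.

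A second reply is that serious events should be rare. The exclusion criteria remove patients with prior thrombosis, cardiovascular disease, liver disease or gallbladder disease. That may well be so, and step 5 shows a loss of only a few points of power at a 1% risk. A reader might infer from the 60% figure that the trial is likely to stop early. The documents do not support that, because they give no event rate. The loss becomes large only if *significant* is read broadly.

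A third reply is that a safety plan may exist elsewhere. The protocol mentions an IRB application, citing it only for the Ferriman–Gallwey calculator and the questionnaires, and it is not among the documents. A reader might conclude that nobody would review the events. The documents show only that no review is described in them. If one exists elsewhere, the protocol sentence should be aligned with it.

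Finally, testosterone is also measured at week 12, so a patient stopped after that visit still contributes data. That softens the loss but does not supply the primary endpoint.

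**Conclusion.** The point holds as a low-cost improvement worth considering. It is not a flaw that undermines the design. Followed as written, the rule ends the trial on two events that may have nothing to do with progesterone, and the word that governs how often this happens is undefined. The probability of meeting the rule runs from 6% to 60% across assumed risks of 1% to 5% with 40 patients at risk. Meeting the rule is not the same as losing the endpoint: a late stop costs little, and an early one leaves too few completers to answer the question. The power figures rest on the plan's own assumption about the standard deviation and on a two-sided test. The sample-size calculation reproduces and is not in question. Confidence is medium, because the event rate and the intended meaning of *significant* are unknown.

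**What to change.** Replace the two sentences with wording such as:

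> A significant adverse event is a severe one, meaning that it prevents usual daily activities. A patient who has a significant or serious adverse event stops study drug and is asked to attend the week-24 visit. When a second patient has such an event, enrolment and dosing are paused at once for all patients. The ethics board reviews relation to study drug, obtaining allocation from the unblinded pharmacist if needed, and decides whether to resume, modify or end the study. A decision to resume states what triggers the next review. The study team and participants stay blinded. Patients whose dosing was interrupted by the pause complete the week-24 visit and are analysed as randomised. If the study is ended, patients still in follow-up give a final testosterone sample at that time.

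The definition is an example. The investigators may choose another, provided the same one governs both the individual and the trial-level rule.

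The cost is a short amendment and the ethics board's agreement to take on the review. A pause may interrupt dosing and so dilute progesterone exposure, and with it the week-24 difference, for some patients. A final sample taken before week 24 does not replace the primary endpoint, but it keeps information that would otherwise be lost. The planned sample size does not change.
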